4.4 Sample size calculation

Our primary outcome of interest is a reduction in nausea, as measured by visual analogue scales (VAS). Currently, no directly comparable studies are available for an accurate sample size calculation, as previous research has not examined the effect of tVNS on nausea severity in healthy participants using VAS scores. However, a randomized controlled trial in patients with chronic nausea and vomiting due to gastroparesis or gastroparesis-like syndrome evaluated nausea improvement after either aprepitant or placebo treatment (23). This study indicated that a reduction in the mean 28-day VAS score from baseline of at least 25 mm was considered a responder. A standard deviation of 21.5 was noted in the treatment group.

The sample size calculation was based on an unpaired-sample t-test (taVNS vs. sham stimulation) with a mean difference of 25 mm and a standard deviation of 21.5. The following parameters were applied: a significance level (alpha) of 0.05 (two-sided) and a power of 0.80. Based on this calculation, we determined that 26 participants are needed. Because non-responders to nausea induction can occur, we will continue enrolment until 26 participants who meet the responder definition for nausea induction (VAS = 50 during induction) have completed the protocol. The calculation can be found at the following web address:

<https://homepage.univie.ac.at/robin.ristl/samplesize.php?test=ttest>

5. TREATMENT OF SUBJECTS

This study aims to investigate the efficacy of taVNS in mitigating nausea caused by intragastric lipid infusion.

5.1 Investigational product/treatment

The intervention of interest is taVNS, with sham stimulation employed as the appropriate control.

5.1.1 taVNS

Electrical stimulation will be administered to the auricular branch of the vagus nerve, specifically at the cymba conchae of the left ear, using a custom-made device called tVNS R (tVNS Health GmbH, Grünwald, Germany). This device has previously been used in the RESILIENCE study (NL84720.068.23/METC 23-032) and comprises a stimulation unit and an ear electrode. This electrode is connected as an anode to the stimulation device by a cable and is worn similarly to an earphone. The stimulation unit sends electrical impulses through the electrode, which stimulates the auricular branch of the vagus nerve. On the test day, subjects assigned to the taVNS group will receive 30 minutes of active stimulation after the nausea induction. According to recent systematic analyses determining the most optimal treatment frequencies for taVNS, the stimulation parameters will consist of biphasic rectangular pulse trains with an impulse frequency of 25Hz, impulse duration of 30 seconds, followed by an impulse pause of 30 seconds, and an impulse width of 450ms (27, 28). Each participant will undergo sensory testing prior to the commencement of the treatment period during which the current will be adjusted to suprathreshold stimulation intensity, with current intensities ranging between 0.25 and 10 mA. The device will indicate stimulation delivery by blinking.

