Participants will arrive at the NUTRIM CRU at Maastricht University after an overnight fast. Compliance with test day regulations will be checked (e.g. fasting, no alcohol). Once compliance is confirmed, the coordinating investigator will properly set up the tVNS device to ensure it can be used immediately after nausea induction. This setup includes adjusting the stimulation current of the tVNS device according to each participant's sensitivity, ensuring it remains below the sensitivity threshold, with current intensities ranging from 0.25 to 10 mA. This is important because active stimulation will be programmed to deliver only subthreshold stimuli. Next, an intravenous cannula will be placed for blood collection. Thereafter, the

investigator (a medical doctor) will manually place a nasogastric tube to facilitate the intragastric infusion of a 50% fat emulsion in water. This method of infusion is selected to replicate the conditions under which dietary fat is ingested as part of a meal. The infusion will be administered at a rate of 5 ml/min, consistent with previous research in which nausea was induced through similar methodologies (1). Participants will be closely monitored throughout the infusion for the onset of nausea, with assessments every 5 minutes using a 0-100 Visual Analogue Scale (VAS) to quantify the nausea severity. Participants will receive clear instructions on how to rate their nausea and indicate its intensity. If a predetermined VAS score of 50/100 is reached, or should the participant start retching, the lipid infusion will be promptly halted to prevent excessive discomfort. Participants will be informed in advance about the 50/100 VAS threshold and provided with guidance on how to interpret and apply this rating. Following the cessation of the infusion, the nasogastric tube will be removed for patient comfort, after which either taVNS or sham stimulation will be administered for 30 minutes.

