The stimulation parameters comprise a biphasic rectangular pulse wave with an impulse frequency of 25Hz, impulse duration of 30 seconds, impulse pause of 30 seconds, and pulse width of 450ms. These parameters have been identified as the most optimal treatment frequencies for taVNS based on systematic reviews (27, 28). Active stimulation will be programmed to deliver only subthreshold stimuli. The device will blink when stimulation is delivered. In the sham (control) group, the electrode will be non-conducting, but the device will still blink to maintain blinding (28). The electrodes used in the tVNS and sham groups differ slightly. Consequently, the investigator responsible for programming the devices will be aware of the treatment allocation, while participants will remain blinded. To ensure double blinding, the randomization code will be altered prior to data analysis, ensuring that the investigator conducting the analysis will be blinded to the treatment allocation. The randomization code will be kept confidential until after the modified intention-to-treat analysis has been reported.

During the stimulation phase, nausea severity will be assessed using a 0-100 VAS score, where 0 indicates “no nausea” and 100 represents the “worst nausea imaginable”. VAS scores will be recorded every 5 minutes, continuing for 30 minutes post-stimulation to evaluate the efficacy of taVNS in alleviating nausea. Additionally, other gastrointestinal symptoms and the desire to eat will be measured at predetermined time points using VAS scores.

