6.4 Summary of known and potential risks and benefits

Transcutaneous vagus nerve stimulation is a non-invasive treatment that is generally well-tolerated and safe in patients without pre-existing cardiac pathology (45, 46). Thus far, no serious risks have been mentioned in the literature. Some studies have reported occasional side effects, such as dizziness or daytime drowsiness during prolonged stimulation, which alleviated upon reducing the stimulation intensity (40). In a pilot study, taVNS exhibited no serious or long-lasting side effects, and no significant heart rate changes were observed during stimulation. Some participants experienced temporary fatigue, concentration difficulties, or a tingling sensation at the stimulation site, which subsided within 90-minutes (47). In a randomized controlled trial involving adolescents, using a more invasive method percutaneous electrical nerve field stimulation, eight individuals discontinued treatment due to aesthetic reasons, discomfort from the device's fit, needle phobia, or anxiety, as well as adhesive allergy (16). However, these concerns are less relevant in the current study, as it employs ear electrodes that fit comfortably without the need for plasters and stimulate the vagus nerve in a non-invasive, transcutaneous manner. In addition, patients may experience slight hearing impairment on the side where the electrode is placed. A recent systematic review and meta-analysis reported no serious adverse effects with taVNS. Mild symptoms of dizziness, headache, and slight redness around the stimulation area were noted, all of which resolved shortly

after discontinuing the intervention (48). Furthermore, taVNS can be provided safely both left and right-sided, as was illustrated by a review article (49).

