8.3.2 Visit 2: Test day

Participants will arrive at the NUTRIM CRU at Maastricht University after an overnight fast. To account for the distinct circadian rhythms of the hormones being measured, the test day is scheduled between 9:00 a.m. and 12:00 p.m. This timing ensures that measurements are taken before the natural ghrelin peak, which typically occurs around noon, optimizing sensitivity to detect any effects of the intervention (61, 62). Although cortisol levels peak around 8:00 a.m. and are still in decline during this window, they are not yet at their most stable (62). However, this is deemed acceptable since cortisol is a secondary outcome. Additionally, this time frame helps minimize the required fasting duration for participants, enhancing both feasibility and comfort.

Upon arrival, all participants will complete a checklist to verify compliance with the test day regulations. These regulations include not eating for at least 6 hours before the test day and not consuming extremely spicy or fatty foods, as well as alcohol, on the day prior to the test day. On the day of the test, participants are only permitted to drink small amounts of water. Additionally, due to the cortisol sampling, participants must refrain from consuming caffeine or engaging in physical exertion on the day of the test day. Participants should also avoid brushing their teeth, chewing gum, or smoking for at least 1 hour before the test session begins.

Once compliance is confirmed, the coordinating investigator will prepare the tVNS device to ensure it is ready for immediate use after nausea induction. This preparation involves adjusting the stimulation current based on each participant's sensitivity, keeping it below the sensory threshold, with current intensities ranging from 0.25 to 10mA.

Following this, the investigator will place an intravenous cannula for blood collection to measure plasma levels of ghrelin and motilin at four different time points.

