e. Analysis of potential effect

The tVNS device is considered safe. Previous studies have shown no serious or long-lasting adverse events (40, 45-47). See paragraph 6.4 'summary of known potential risks and benefits' for previously reported risks.

f. Pharmacokinetic considerations

Not applicable.

g. Study population

All participants are healthy volunteers aged 18-65 years. No risks have been identified for this population (see also paragraph 6.2). Vagus nerve stimulation has been applied to both healthy controls and patient populations for several years (56-59).

h. Interaction with other products

Not applicable.

i. Predictability of effect

Not applicable.

j. Can effects be managed?

In healthy humans, taVNS has been demonstrated to be a safe and well-tolerated procedure, particularly in individuals without a history of cardiac disease (37, 45, 46). Subjects with cardiac pathology or pacemakers will be excluded from the study. However, autonomic parameters will be monitored continuously throughout the taVNS stimulation and nausea induction period. No serious complications have been reported in literature. A few subjects have reported dizziness, fatigue, concentration problems and a tingling sensation at the ear, which are typically associated with longer stimulation durations or with higher stimulation intensities (47). Therefore, prior to the experiment, the stimulation current will be adjusted according to each subject's sensitivity to ensure it remains below the pain threshold. Participants are allowed to withdraw from the study at any time.

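### Section 5.1.1 sets the active current above the sensory threshold, while sections 3 and 8.3.2 keep it below; 5.1.1 is most likely the error

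*Protocol*

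**What the plan says.** The protocol describes how the active current is set in four places.

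- **Section 5.1.1 (taVNS)**, the definition of the intervention: participants have sensory testing before treatment, at which "the current will be adjusted to suprathreshold stimulation intensity, with current intensities ranging between 0.25 and 10 mA".
- **Section 3 (Study design, Visit 2)**: the device is set to each participant's sensitivity, "ensuring it remains below the sensitivity threshold, with current intensities ranging from 0.25 to 10 mA". The next sentence adds: "This is important because active stimulation will be programmed to deliver only subthreshold stimuli". Later in section 3, with the pulse parameters, the rule appears again: "Active stimulation will be programmed to deliver only subthreshold stimuli".
- **Section 8.3.2 (Visit 2: Test day)**, the step-by-step procedure: the current is adjusted to the participant's sensitivity, "keeping it below the sensory threshold, with current intensities ranging from 0.25 to 10mA".
- **Section 13.1, item j (risk analysis)**: the current is adjusted to sensitivity "to ensure it remains below the pain threshold".

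On the comparator, section 5.1.2 specifies a non-conducting electrode at the same ear site. Sections 5.1.2 and 8.2 rest participant blinding on the shared location and a device that blinks in both arms. The investigator who programs the device knows the allocation.

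**The concern.** The intensity setting is in effect the dose of the investigational treatment. An operator working from 5.1.1 would deliver a current that can be felt; one working from 8.3.2 would deliver one that cannot. Those are different interventions under one name.

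The second consequence is for blinding. Sham participants receive no current and so have nothing to feel. The protocol itself reports that stimulation can be noticed: section 6.4 mentions "a tingling sensation at the stimulation site, which subsided within 90-minutes", and section 13.1 item j lists "a tingling sensation at the ear, which are typically associated with longer stimulation durations or with higher stimulation intensities". If active participants felt the current, the shared site and the blinking light would not conceal it. The primary outcome is the participant's own nausea rating on a 0-100 scale. Because the programming investigator is already unblinded, the participant's blinding is the main protection for that rating during the session.

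**Working it through.** The point is textual, so the check is to set every statement of intensity side by side.

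| Place | Setting stated | Range stated |
|---|---|---|
| 3, Visit 2 set-up | below the sensitivity threshold | 0.25-10 mA |
| 3, Visit 2 set-up, next sentence | subthreshold only | none |
| 3, stimulation parameters | subthreshold only | none |
| 8.3.2, test-day procedure | below the sensory threshold | 0.25-10 mA |
| 5.1.1, definition of taVNS | suprathreshold | 0.25-10 mA |
| 13.1 item j | below the pain threshold | none |

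**Are these the same setting?** Yes. Sections 3, 5.1.1 and 8.3.2 all describe an adjustment made for each participant before stimulation, and all three give the same current range. Section 3 speaks of sensitivity and 8.3.2 of sensory threshold. I treat the two as the same, which fits the subthreshold wording that follows in section 3.

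**Which is intended?** The count is four subthreshold statements to one suprathreshold. The three in section 3 are near repetitions, so it is fairer to say two sections against one. Section 3 marks the subthreshold setting as deliberate, and 8.3.2 is the text an operator would follow on the day. Both favour subthreshold.

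**Does 13.1 item j decide it?** No. A current below the sensory threshold is normally also below the pain threshold, but so is one that is felt without hurting. The phrase fits either rule.

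**Does anything else reconcile the texts?** No. Section 5.1.1 does not say that the current is lowered after testing, and no other section explains the difference.

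**Does any figure depend on it?** No. The sample size in section 4.4 uses a difference of 25 mm, SD 21.5, two-sided alpha 0.05 and power 0.80. With n per arm, the noncentrality is (25/21.5)/sqrt(2/n) on 2n - 2 degrees of freedom:

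- n = 12: 1.163/0.408 = 2.85 on 22 df, power 0.777
- n = 13: 1.163/0.392 = 2.96 on 24 df, power 0.812

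Thirteen per arm gives 2 x 13 = 26, as stated. Correcting the intensity wording leaves this unchanged.

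**The case against.** The best defence is grammatical. The clause in 5.1.1 can be attached to the sensory testing, so that it describes raising the current until it is felt, which is how a threshold is found. Sections 3 and 8.3.2 would then give the treatment setting, and 5.1.1 would be incomplete rather than contradictory. This may well be what the authors had in mind. It does not rescue the sentence, which says the current is adjusted to that level and stops there. A reader of 5.1.1 alone would set it above threshold.

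A second argument is that the practical risk is small: the test-day procedure is right, and its subthreshold rule is itself what prevents a felt cue during treatment. That stands as a limit on the concern. The harm arises only if someone follows 5.1.1 over 3 and 8.3.2. It is also the reason not to leave a contrary instruction in the section that defines the treatment.

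Two further points stand in part. The wording in 13.1 item j is a safety statement and does not conflict with the subthreshold rule, so aligning it is desirable but secondary. And the sentence in section 3 that calls the set-up important restates the rule without saying why subthreshold was chosen. It shows intent, not a rationale.

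**Conclusion.** The contradiction is real: one setting, over one current range, is given in opposite terms in current body text. That 5.1.1 is the faulty text is an inference, but a well-supported one; only the sponsor can confirm it.

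The threat to blinding is plausible but not quantified. The protocol offers nothing from which to estimate how many participants would guess their arm or how far their ratings would shift. The threat assumes that a suprathreshold current is noticeable, which follows from the term and fits the tingling the protocol reports, and that 5.1.1 is the text followed. The sample size, endpoint and planned model are untouched.

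Correcting 5.1.1 removes the instruction that would create a felt cue during treatment. It does not by itself show that blinding is secure. Section 8.2 places randomisation before the test day, and 5.1.1 has every participant sensory-tested. If testing uses the allocated electrode, which the protocol does not state, the test itself could give a cue. That is a separate, conditional point and adds nothing to the weight of this one. The correction should be made.

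**What to change.** Reword the sentence in 5.1.1 to say that sensory testing establishes each participant's sensory threshold and that the current is then set below it for the whole treatment period, as sections 3 and 8.3.2 already require. Preferably replace the reference to the pain threshold in section 13.1 item j with the same rule, so that the protocol uses a single wording.

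The cost is one sentence and one phrase, with no added visits, staff or measurements.

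If the sponsor does intend suprathreshold stimulation, the statements in sections 3 and 8.3.2 must change instead, and the participant-blinding claims in 5.1.2 and 8.2 must be revised. Only in that case is the cost more than editorial.

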5.1.2 Sham stimulation

In the control group, sham stimulation will be administered to the same electrode location (left cymba conchae) using an identical device as that used for taVNS. The electrode used for sham stimulation will be non-conducting, ensuring that there is no stimulation of the vagus nerve. Although the devices for tVNS and sham stimulation appear identical, the electrodes for each group are slightly different. Consequently, the investigator responsible for programming the devices will be aware of the treatment allocation. Participants will not be aware of the treatment received since stimulation is provided to the same location, and the device will still blink during both types of stimulation to maintain blinding (28). The randomization code will be altered

before analysis, ensuring that the investigator conducting the data analysis remains unaware of the treatment allocation. The randomization code will be kept confidential until after the modified intention-to-treat analysis has been reported.

5.2 Use of co-intervention

5.2.1 Intragastric lipid infusion

As a co-intervention, an intragastric infusion of a 50% fat emulsion in water will be administered to induce nausea. A 10-F gauge single-lumen polyurethane nasogastric tube (Nutricair Enteral-Enfit, Charrière 10) will be manually inserted by the coordinating investigator, positioning the catheter in the stomach and connecting it to a nutrition enteral delivery pump (Applix Smart pomp). A 20/60ml Nutricair Enteral-Enfit syringe will be used to administer the fat emulsion through the feeding tube. Standard clinical protocols for nasogastric tube placement will be followed, including a pH measurement to verify the tube's position, ensuring participant's safety and comfort.

The fat emulsion (Calogen, NUTRICIA, Netherlands) used is comparable to that employed in previous research on intragastric nausea induction (1). It is a medical nutritional product typically used to address an 'energy deficit' in patients who are unable to meet their recommended energy intake through regular food and/or oral nutritional supplements. The emulsion is suitable for enteral use and can be administered via a nasogastric tube (31). See D6.1_SPC_Calogen_Versie1.0_dd 16-10-2024 & D6.2_Calogen_Voedingstabel_Versie1.0_dd 15-10-2024 for additional information.

The fat emulsion consists of 50% long-chain triglyceride and 50% water (osmolality: 0 mOsm/L, Calogen, NUTRICIA, Netherlands). Previous research has shown that long-chain triglycerides elicit a stronger nausea response than medium-chain triglycerides, which is why long-chain triglycerides were selected as the primary component (1). The infusion rate will be set at 5 ml/min (22.5 kcal/min) and will continue until the participant experiences nausea, indicated by a VAS score of 50/100 (1). Based on previous studies, it is expected that approximately 258 + 32 ml of the fat emulsion is required to induce nausea through gastric relaxation, with the process taking approximately 52 ± 6 minutes (1). If the nausea score does not reach the VAS of 50/100 after 1.5 hours of infusion, the infusion will be discontinued, and the test day will be terminated. In this case, the participant will be considered a drop-out due to non-response to the nausea-inducing stimulus.

Participants will be closely monitored throughout the procedure to ensure their safety, and nausea severity will be assessed using validated scales. For a detailed description of the procedure, please see F4.1_Nasogastric_Tube_Placement_SOP_Versie1.0_dd 14-10-2024 and paragraph 8.3.

5.3 Escape medication

To ensure participant safety, an ondansetron dissolvable tablet will be administered as escape medication when nausea reaches a severity level of 80 or higher out of 100 on the VAS scale, indicating severe discomfort and an imminent vomiting sensation. Following the immediate termination of the lipid infusion, a single dose of 4 mg will be given, with a maximum of four doses (16mg total) allowed per day if necessary. Based on previous research using more intensive nausea induction methods, including intraduodenal lipid infusion and gastric distension, in which 2 out of 12 healthy participants experienced vomiting, we do not expect frequent vomiting in our study (10).

Ondansetron is a well-established anti-emetic that exerts its effects primarily through antagonism of 5HT₃ (serotonin) receptors. It is commonly used for the management of nausea in clinical settings (32). See D6.4_Ondansetron_SPC_Versie1.0_dd 22-07-2024 for additional information.

Given that participants will be healthy volunteers, it is anticipated that no contraindications, such as relevant medication use, will be present. However, if ondansetron is administered, participants will be closely monitored for both relief from nausea and potential side effects, including headache, dizziness, and other known reactions, for at least 1 hour following administration.

The decision to administer ondansetron will be documented, including the time of administration, the participant's reported nausea level, and any subsequent symptoms.

